8.2.1. Inclusion criteria

Patients must meet all of the following inclusion criteria to be eligible for inclusion in the study:

1. A diagnosis of metastatic breast cancer, based on the National/MHS cancer registry.
2. Newly diagnosed metastatic breast cancer patients and newly treated with palbociclib within 6 months of diagnosis, in any line of treatment in the metastatic setting.
3. Available data on palbociclib treatment for at least 6 months.
4. Continuous healthcare plan enrolment in MHS for at least one year before index date.
5. At least 18 years of age at index date.

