Genetic testing for gBRCAm performed	MHS structured data	Baseline characteristic	Baseline	Reported	yes/no
Death	MHS structured data	Endpoint	After index date		Death is captured from National Insurance Data
Disease Characteristics					
Date of initial breast cancer diagnosis	National cancer registry	Baseline characteristic	Baseline	Reported	Records may be incomplete
Histology	Extracted from PDF patient data files	Baseline characteristic	Baseline	Reported	
Location of metastases	Extracted from PDF patient data files	Baseline characteristic	Baseline	Reported	Bone, brain, lymph nodes, ovary, visceral
Visceral/non visceral status	Extracted from PDF patient data files	Baseline characteristic	Baseline	Reported	Non-visceral, visceral (lungs, liver), bone only
Eastern Cooperative Oncology Group (ECOG) performance status at diagnosis	Extracted from PDF patient data files	Baseline characteristic	Baseline	Reported	Grouped as 0-1, 2, 3-4, unknown/missing
Molecular status data: performed HER2/ HR tests	Extracted from PDF patient data files	Baseline characteristic	Baseline	Reported	yes/no
Hormone sensitivity	Extracted from PDF patient data files	Baseline characteristic	Baseline	Reported	primary or secondary resistance
Variable	Source	Role in study	Period of measurement	Reporting phase	Operational definition
Progression of disease from imaging	Extracted from PDF patient data files	Baseline characteristic	Baseline	Reported	
Treatment Characteristics					

Index treatment regimen	MHS structured data	Treatment characteristic	Study observation period	Reported	Palbociclib combination treatment - combination with aromatase inhibitor or fulvestrant.
Lines of therapy	MHS structured data and PDF patient data files.	Treatment characteristic	Study observation period	Reported	Identified according to the sequence of dispensed medications.
Median duration of each line of therapy	MHS structured data	Treatment characteristic	Study observation period	Reported	Duration in weeks or months between the start and stop of each line of therapy will be reported as mean (SD) and median (IQR)
Number of cycles of index treatment	MHS structured data	Treatment characteristic	Study observation period	Reported	Mean (SD) and Median (IQR)
Index palbociclib treatment dose	MHS structured data	Treatment characteristic	Study observation period	Reported	Mean (SD) and Median (IQR)

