- Number (N) (%) patients receiving first, second- and third-line treatments by drug name and therapeutic group, median duration of each line of therapy, and number of cycles for each line of therapy. Treatment lines are defined according to the sequence of dispensed medications, with information captured both from pharmacy database (for medications approved by the HMO), and from hospital medical records (including information on medications provided by private insurance and clinical studies) using the following algorithm. Any drug purchased within 1 month of a new line is considered part of that line. Cessation of a drug from a combination regimen is considered the same line as the patient is not receiving additional treatment. Cessation is likely due to tolerance issues or adverse effects although we do not know the reason as our data is from purchase data. Addition of a new drug to a current regimen is considered a new treatment line.
- Index treatment regimen - palbociclib combination partner: Aromatase Inhibitors (AI) or fulvestrant; Subsequent therapy per lines of therapy.
- Dosing and dose changes, interruptions, delays, and discontinuations associated with palbociclib therapy.
- Treatment lines will be rerun for extended follow up to 30 June 2022.

8.3.4. Cancer related variables:

These variables will be extracted from patient PDF files/ letters sent to MHS from the physician.

- Date of initial breast cancer diagnosis.
- Histology.
- Location of metastases: bones, brain, visceral, lymph nodes, other.

- ECOG performance status at diagnosis.
- Molecular status data: performed HER2/ HR tests (yes/no).
- Hormone sensitivity: primary or secondary resistance.
- Progression of disease from imaging.

8.3.5. Clinical outcomes for palbociclib (analysed separately by therapy line):

- N (%) progression at 6, 12 and 24 months.
- Duration of treatment on palbociclib (Median time on treatment).
- Time on treatment for subsequent line of therapy.
- Time to chemotherapy after palbociclib treatment.

■ CCI [REDACTED]

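### Median duration and cycles are reported for every line of therapy, but the six-month entry window caps any metastatic line given between diagnosis and palbociclib, so for those lines the figure describes the entry rule

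*Combined protocol and SAP*

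**What the plan says.** Section 8.3.3 lists the number and percentage of patients on first-, second- and third-line treatment, by drug and therapeutic group, with "median duration of each line of therapy, and number of cycles for each line of therapy". The matching row of the section 8.3 variable table says: "between the start and stop of each line of therapy will be reported as mean (SD) and median (IQR"). Neither place limits the statistic to the palbociclib line or to later lines. The row gives its measurement period as the study observation period, which is not defined.

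The index date is the start of palbociclib (section 8.2). Inclusion criterion 2 (section 8.2.1) requires patients to be "newly treated with palbociclib within 6 months of diagnosis, in any line of treatment in the metastatic setting". Criterion 3 asks for "Available data on palbociclib treatment for at least 6 months".

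Two line rules in section 8.3.3 matter here: "Any drug purchased within 1 month of a new line is considered part of that line", and "Addition of a new drug to a current regimen is considered a new treatment line".

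Section 8.1 includes treatment history among the data captured. The baseline shells in Annex 1 have columns for palbociclib as first, second and third line, so the plan expects some patients to have had earlier lines.

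**The concern.** In a patient whose palbociclib is second or third line, the earlier metastatic lines are pre-index lines. Under criterion 2 they must all fit between the metastatic diagnosis and palbociclib start. None can be ongoing, and none that begins after the diagnosis can exceed 6 months. A patient whose first metastatic line lasted longer is not in the cohort. This is right truncation of the duration by the entry rule. It is not censoring, and longer follow-up does not cure it.

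The line algorithm adds to the problem. An endocrine drug started more than a month before palbociclib becomes a line of its own, closed by the addition of palbociclib, so it counts as a short completed first line.

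Line duration is a reported treatment-pattern result. A reader who saw a first-line endocrine or chemotherapy drug with a median under 4 months would take it for a finding about the drug, when the entry window produced it. Lines that start at or after index have far longer potential follow-up, so lines with the same number would not be comparable.

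**Working it through.** The plan states no expected duration, no line mix and no sample size calculation, so there is no figure of its own to reproduce. Only the 6-month window and the dates below come from the documents. All true durations, distributions and shares are assumptions.

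**Follow-up after index.** From 31 August 2020 to 30 June 2022 is 21.9 months, and from 1 January 2018 to 30 June 2022 is 53.9 months. Lines starting at index can be observed for about 22 to 54 months (before death or leaving the health plan). A pre-index line has at most 6.

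**Step 1: a single pre-index line, exponential.** With true median m, λ = ln 2 / m and F(6) = 1 − exp(−6λ). The median among lines that end within 6 months is −ln(1 − F(6)/2) / λ. For m = 12: λ = 0.0578, F(6) = 0.293, and the median is 0.158 / 0.0578 = 2.7 months.

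| True median (months) | Share ending within 6 months | Reported median (months) |
|---|---|---|
| 6 | 50% | 2.5 |
| 12 | 29% | 2.7 |
| 18 | 21% | 2.8 |
| 24 | 16% | 2.9 |

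With two prior lines inside the window, each has a median of about 1.6 to 1.7 months (simulated for true medians of 6 to 18 months).

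**Step 2: sensitivity to the distribution.** By simulation, with the line starting 0 to 1 month after diagnosis and ending by month 6, for true medians of 6, 12 and 24 months:

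- exponential: 2.3, 2.5 and 2.6 months
- Weibull, shape 1.5: 3.1, 3.3 and 3.4 months
- Weibull, shape 2: 3.6, 3.8 and 3.9 months

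A fourfold change in the true median moves the reported one by about 0.3 months in each case. The assumed shape matters more than the true duration.

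**Step 3: a pooled first-line median.** Let s be the share of patients with palbociclib in line 2 or later, and M the true median of first-line palbociclib (exponential). Every pre-index first line has ended by 6 months. So whenever the pooled median exceeds 6 months it solves s + (1 − s)(1 − 2^(−t/M)) = 0.5, which gives t = M × log2(2(1 − s)). If criterion 3 means at least 6 months on palbociclib, first-line palbociclib times below 6 months are removed and, for an exponential, t rises by 6. With M = 20:

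| s | Criterion 3 does not restrict time on drug | Criterion 3 requires 6 months on drug |
|---|---|---|
| 0% | 20.0 | 26.0 |
| 10% | 20 × log2(1.8) = 17.0 | 23.0 |
| 20% | 20 × log2(1.6) = 13.6 | 19.6 |
| 30% | 20 × log2(1.4) = 9.7 | 15.7 |

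Kaplan-Meier simulation with censoring uniform over 22 to 54 months agrees with these values to within about 0.1 month. Within each column pooling lowers the median. Against the assumed true 20 months, however, the right-hand column is above at 10%, about equal at 20% and below at 30%.

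**The case against.** A reader might infer that the overall first-line median will come out far too short. The documents do not support that. They do not give the share of later-line entrants, and the entry window itself holds that share down: under the exponential assumption only 16% to 29% of prior lines with a true median of 12 to 24 months end in time. Section 8.3.3 reports lines by drug name and therapeutic group, so a pre-index endocrine line need not be merged with palbociclib. One reading of criterion 3 pushes the other way and can offset or reverse the net bias. All of this stands.

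It can also be said that pre-index lines may not be meant at all. Other variables measured over the study observation period, such as time to next treatment and time to chemotherapy, run from index or later, whereas history variables are marked as baseline or prior history. That makes the text ambiguous. But treatment history is collected, first-line treatment is listed without restriction, and subsequent therapy appears in a separate bullet, so counting all lines is the natural reading.

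Nor is the cap absolute for every pre-index line. Line 1 is not explicitly anchored at the metastatic diagnosis, so a drug begun before that diagnosis and continued could show a longer duration.

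Finally, palbociclib outcomes are analysed separately by therapy line, and the Annex shells for time on treatment and treatment patterns cover palbociclib only. A reader might infer that those results are contaminated by pre-index lines; they are not.

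**Conclusion.** The concern holds for metastatic lines that start after the metastatic diagnosis and before palbociclib. Criterion 2 limits them to 6 months, and their median as specified would be about 2.3 to 3.9 months for assumed true medians of 6 to 24 months. The cap follows from the plan's text. The values within it rest on assumed exponential or Weibull durations and, for that range, a line start within a month of diagnosis.

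A pooled first-line median would mix these truncated times with palbociclib times that criterion 3 may select in the opposite direction. It would be hard to interpret even if the two effects happened to cancel, but its net error can be small, large or reversed. Two uncertainties remain: the undefined observation period, and lines begun before the metastatic diagnosis. They limit how many lines are affected but do not remove the problem. Section 8.9 does not mention it, and says instead that selection bias is minimised because the study aims to include all metastatic patients treated in the period.

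**What to change.** - Define the study observation period in section 8.3, and say whether it includes time before index.
- In section 8.3.3 and the duration row of section 8.3, restrict duration and number of cycles to lines that start at or after the index date.
- Describe pre-index lines by drug and N (%) only. If their durations are wanted, put them in a separate table labelled as limited by the entry window, and never pool them with index or post-index lines of the same number.
- State the truncation in section 8.9.
- Reconcile criterion 2 with section 7, which covers all lines of therapy, and with section 8.9, which speaks of including all metastatic patients. If the authors conclude that the 6-month window was not intended, this truncation goes with it and the label must change accordingly.

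The cost is a few sentences and one filter on line start date, with no new data. The downside is that durations of pre-palbociclib lines are no longer a main result.

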8.2. Setting

Patients (age \geq 18 years) will be identified from MHS purchase data between 01 July 2017 until 31 August 2020.

Index date will be defined as date of initiation of palbociclib treatment.

Patient records must meet the following criteria to be eligible for the medical record reviews. Patients must be at least 18 years of age at index date and they must have been diagnosed with HR+/HER2- ABC/ MBC. Patients must have received palbociclib combination in line with Israel approved indications. A minimum of 6 months follow up of palbociclib combination therapy prior to date of medical record review will be necessary for inclusion. This will permit the capture of meaningful clinical outcomes data. Patients will be followed through the end of the observation period, date of death or left the health maintenance organization (HMO).

A full list of the inclusion criteria can be found in Section 9.2.1.

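### The line algorithm can label palbociclib as second line when it joins an ongoing first-line endocrine partner more than 1 month after that partner started, without progression

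*Combined protocol and SAP*

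**What the plan says.** Section 8.3.3 sets out the algorithm. "Treatment lines are defined according to the sequence of dispensed medications", taken from the pharmacy database and from hospital records. Three rules follow:

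- Grouping: "Any drug purchased within 1 month of a new line is considered part of that line".
- Stopping: "Cessation of a drug from a combination regimen is considered the same line as the patient is not receiving additional treatment".
- Adding: "Addition of a new drug to a current regimen is considered a new treatment line".

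The variables table in Section 8.3 defines the index regimen as a combination: "Palbociclib combination treatment - combination with aromatase inhibitor or fulvestrant". Section 8.2 fixes time zero: "Index date will be defined as date of initiation of palbociclib treatment". Criterion 2 in Section 8.2.1 admits patients "newly treated with palbociclib within 6 months of diagnosis, in any line of treatment in the metastatic setting".

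The line label is used widely. Section 8.3.5 is headed "Clinical outcomes for palbociclib (analysed separately by therapy line") and covers progression at 6, 12 and 24 months, time on palbociclib, time on the subsequent line and time to chemotherapy. Annex Tables 1 to 4 are all laid out by line, and Table 3 has a log-rank P value.

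**The concern.** The study treats palbociclib plus an endocrine partner as one regimen, but the algorithm can split that regimen in two. If the partner is dispensed first and palbociclib more than 1 month later, the adding rule opens a new line. The partner alone becomes a short first line and the index combination becomes second line, although the disease need not have progressed. By the same logic, a true second-line patient who adds palbociclib late becomes third line.

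A second-line group that contains first-line patients no longer describes second-line use. If those patients stay on treatment longer than true second-line patients, the labelled second-line median rises and the strata move towards each other. The log-rank test in Table 3 then compares mixed groups. The durations reported per line also gain short first lines that did not end in treatment failure.

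**Working it through.** The plan has no figure that depends on the line rule and no sample size calculation, so there is nothing to reproduce. The check has three steps.

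**Step 1: apply the rule literally.** Let g be the gap in months from the start of the endocrine partner for metastatic disease to palbociclib. Under Section 8.3.3 the label is line 1 if g ≤ 1 and line 2 if g > 1.

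| g (months) | 0 | 0.5 | 1 | 1.5 | 2 | 3 | 5 | 6 |
|---|---|---|---|---|---|---|---|---|
| Label | 1 | 1 | 1 | 2 | 2 | 2 | 2 | 2 |

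Progression does not enter the rule.

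**Step 2: can such patients enter?** Yes. Criterion 2 bounds the interval from diagnosis to palbociclib at 6 months, so gaps above 1 month and up to 6 months are eligible. The variables table also foresees regimens whose drugs start on different dates.

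**Step 3: how large could the effect be?** From the document: N = 500 to 700 (Section 8.5). Assumed, with no basis in the documents:

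- true first- and second-line shares s1/s2 of 60%/25% or 70%/20%;
- late-add fraction f among true first-line patients of 0% to 20%;
- exponential time on palbociclib with medians of 24 months (first line) and 12 months (second line);
- late-add patients have the same outcome as other first-line patients.

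Formulas:

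- moved = f × s1 × N
- contamination w = f·s1 / (s2 + f·s1), which does not depend on N
- labelled second-line median m solves (1 − w)·2^(−m/12) + w·2^(−m/24) = 0.5

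Example, N = 500, 60%/25%, f = 20%: moved = 0.20 × 300 = 60; w = 60 / (125 + 60) = 32.4%; m = 14.8 months.

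| f | Moved, N = 500 | Moved, N = 700 | w | Labelled second-line median (true 12) |
|---|---|---|---|---|
| 0% | 0 | 0 | 0% | 12.0 |
| 5% | 15 to 18 | 21 to 25 | 11% to 15% | 12.8 to 13.2 |
| 10% | 30 to 35 | 42 to 49 | 19% to 26% | 13.5 to 14.1 |
| 20% | 60 to 70 | 84 to 98 | 32% to 41% | 14.8 to 15.7 |

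For a given f, w grows as the true second-line share shrinks. Criterion 2 may make that share small, because a true second-line patient must start and leave a first metastatic line and begin palbociclib within 6 months of diagnosis.

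For scale, the approximate 95% half-width of the labelled second-line median without censoring is 1.96 × 0.5/√n divided by the density at the median. In the example, n = 185 and the density is 0.0227, giving 0.0721/0.0227 = 3.2 months. Across both values of N and both splits it is 2.6 to 3.5 months for f of 5% to 10% and 2.7 to 3.5 months for f of 20%. The shifts are 0.8 to 2.1 months and 2.8 to 3.7 months respectively.

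**The case against.** A prespecified dispensing rule is a normal choice for a descriptive database study without a comparator, and Section 8.9 already acknowledges misclassification. Criterion 2 excludes most patients on long-standing metastatic endocrine therapy who were waiting for reimbursement, so only gaps between 1 and 6 months matter. The documents do not say that approval takes more than a month. The late-add fraction is unknown, every outcome input above is assumed, and at 5% to 10% the illustrated shift lies inside the sampling error.

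These points limit the size of the problem but do not remove it. The written rule gives the wrong label to any eligible late-add patient, and unlike sampling error the resulting shift does not shrink with N.

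Four stronger readings are tempting but not supported:

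- **That every line-stratified outcome is misclassified.** Each is exposed, but only late-add patients change stratum. Total columns do not change, and the palbociclib clock starts at palbociclib initiation whatever the label.
- **That non-cancer drugs would open a line.** The rule sits under treatment patterns by drug and therapeutic group, and co-medications are a separate variable.
- **That charts play no part in line assignment.** Hospital records and PDF files supply medication data to it. What is missing is a progression condition.
- **That exchanging the endocrine partner while palbociclib continues necessarily creates a false time-to-next-treatment (TTNT) event.** Section 8.3.3 covers adding and stopping but does not name substitution. TTNT is defined by the next line, not by progression. The handling is unstated rather than shown to be wrong.

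**Conclusion.** The concern holds for late-add patients. Followed as written, the algorithm can split the study's own index combination and place unprogressed first-line patients in the second-line stratum of the Section 8.3.5 outcomes and Annex Tables 1 to 4. The mechanism follows from the text alone and needs no assumption.

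The size cannot be determined from the documents. The illustrative range of 11% to 41% contamination for f of 5% to 20% rests on the assumed line shares. The median shifts also rest on the assumed medians, exponential times and exchangeability of late-add with other first-line patients. At f = 0 nothing changes. The plan should be corrected before the line-specific results are produced; results for the whole cohort are not in question on this point.

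**What to change.** Amend Section 8.3.3 and the analysis specification as follows:

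1. For the analysis, give palbociclib that joins an ongoing endocrine partner started for metastatic disease the same line number as that partner, unless the chart documents progression in between.
2. Say that this changes the line label only and that the index date stays at palbociclib initiation. Otherwise the variables table's rule of taking the first date of a multi-drug regimen could move the clock back to the partner's start and add time that every late-add patient has survived by design.
3. State how exchange of the endocrine partner while palbociclib continues is numbered, and whether it counts as a TTNT event.
4. Report the number and percentage of patients with a gap over 1 month.
5. Give the line-specific results under the present 1-month rule and under a longer window as sensitivity analyses.

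The cost is modest: some wording, one derivation and repeated tables. Lines are being rerun to June 2022 anyway, and progression from imaging is already on the list of items taken from the PDF files. That item has no operational definition, so the sponsor should confirm that extraction covers the interval before palbociclib and records dates. Some cases will rest on incomplete letters, and a default for those should be stated.

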8.4. Data sources

Data will be extracted from the Maccabi Health Services (MHS) database. MHS is a nationwide health plan (payer-provider) representing a quarter of the population in Israel. The MHS database contains longitudinal data on a stable population of 2.2 million people since 1993 (with <1%/year moving out). Data are automatically collected and include comprehensive laboratory data from a single central lab, full pharmacy prescription and purchase data, and extensive demographic data on each patient. MHS uses the International Classification of Diseases, Ninth Revision, Clinical Modification (ICD-9-CM) coding systems as well as self-developed coding systems to provide more granular diagnostic information beyond the ICD codes. Medications are coded according to the Israeli coding system with translations to Anatomical Therapeutic Chemical (ATC) coding system wherever available. Procedures are coded using Current Procedural Terminology (CPT) codes.

